10.11. Appendix 11: Abbreviations

The following is a list of abbreviations that may be used in the protocol.

Abbreviation	Term
6MWD	6-Minute Walk Distance
6MWT	6-Minute Walk Test
ADA	anti-drug antibodies
ADL	activity/activities of daily living
AE	adverse event
AKI	acute kidney injury
ALT	alanine aminotransferase
AST	aspartate aminotransferase
AUC _{inf}	area under the serum concentration time profile from time zero extrapolated to infinite time
AUC _{last}	area under the serum concentration time profile from time zero to the time of the last quantifiable concentration
AUC _{tau}	area under the serum concentration-time curve over the dosing interval tau
AV	atrioventricular
β-hCG	β-human chorionic gonadotropin
BD	business day
BP	blood pressure
bpm	beats per minute
C _{avg}	average concentration
CFR	Code of Federal Regulations
CIOMS	Council for International Organizations of Medical Sciences
CK	creatinine kinase
CKD-EPI	chronic kidney disease epidemiology
CL/F	apparent clearance
CLIA	Clinical Laboratory Improvements Amendments
C _{max}	maximum observed concentration
CONSORT	Consolidated Standards of Reporting Trials
COPD	chronic obstructive pulmonary disease
COVID-19	coronavirus disease 2019
CRF	case report form
CRO	contract research organization
CSR	Clinical Study Report
CSS	Clinical Summary Score
CT	computed tomography;clinical trial
CTIS	Clinical Trial Information System
CTR	Clinical Trials Regulation
CYP	cytochrome P450

Abbreviation	Term
DCT	data collection tool
DDI	drug-drug interaction
DILI	drug-induced liver injury
DU	dispensable unit
EC	ethics committee
ECG	electrocardiogram or electrocardiography
eCOA	electronic clinical outcome assessment
eCrCl	estimated creatinine clearance
eCRF	electronic case report form
EDB	exposure during breastfeeding
E-DMC	External Data Monitoring Committee
EDP	exposure during pregnancy
eGFR	estimated glomerular filtration rate
E _{max}	maximal effect
EOT	end of treatment
eSAE	electronic serious adverse event
EU	European Union
EudraCT	European Union Drug Regulating Authorities Clinical Trials (European Clinical Trials Database)
FDA	Food and Drug Administration
FSH	follicle-stimulating hormone
F/U1	follow-up visit 1
F/U2	follow-up visit 2
GCP	Good Clinical Practice
GDF-15	growth differentiation factor 15
GGT	gamma-glutamyl transferase
HDL	high-density lipoprotein
HF	heart failure
HFrEF	heart failure with reduced ejection fraction
HR	heart rate
HRQL	health-related quality of life
HRT	hormone replacement therapy
hsCRP	high-sensitivity C-reactive protein
IB	Investigator's Brochure
ICD	informed consent document
ICH	International Council for Harmonisation of Technical Requirements for Pharmaceuticals for Human Use
ID	identification
IgG	immunoglobulin g
IMP	investigational medicinal product
IND	Investigational New Drug

Abbreviation	Term
INR	international normalized ratio
IP	investigational product
IPAL	Investigational Product Accountability Log
IPM	investigational product manual
IRB	Institutional Review Board
IRC	internal review committee
IRT	Interactive Response Technology
KCCQ-23	Kansas City Cardiomyopathy Questionnaire
KDIGO	Kidney Disease: Improving Global Outcomes
LBBB	left bundle branch block
LDL	low-density lipoprotein
LFT	liver function test
LLOQ	lower limit of quantitation
LVEF	left ventricular ejection fraction
mAbs	monoclonal antibodies
MI	myocardial infarction
MIC-1	Macrophage Inhibitory Cytokine 1
MMRM	mixed models repeated measures
MQI	medically qualified individual
N/A	Not Applicable
NAb	neutralizing antibodies
NIMP	noninvestigational medicinal product
NOAEL	no observed adverse effect level
NSCLC	non-small cell lung cancer
NT-proBNP	N-terminal pro-B type natriuretic peptide
NYHA	New York Heart Association
OSS	Overall Summary Score
PAX	paired box
PCD	primary completion date
PD	pharmacodynamic(s)
PGI-C	Patient Global Impression of Severity
PGI-S	Patient Global Impression of Change
PK	pharmacokinetic(s)
PR	pulse rate
PRO	patient reported outcomes
PROMIS	Patient-Reported Outcomes Measurement Information System
PSSA	Pfizer's Serious Adverse Event Submission Assistant
PTR	peak-to-trough ratio
PVC	premature ventricular contraction
Q3W	every three weeks
Q4W	every four weeks

Abbreviation	Term
QTc	corrected QT interval
QTcF	QTc corrected using Fridericia's formula
QTL	quality tolerance limit
RBC	red blood cell
RNA	ribonucleic acid
SAE	serious adverse event
SAP	Statistical Analysis Plan
SC	subcutaneous(ly)
Scr	serum creatinine
SD	standard deviation
SoA	schedule of activities
SOP	standard operating procedure
SRSD	single-reference safety document
SSID	single subject identifier
SUSAR	Suspected Unexpected Serious Adverse Reaction
SV1	Screening visit 1
SV2	Screening visit 2
$t_{1/2}$	terminal elimination half-life
T bili	total bilirubin
TEAE	treatment-emergent adverse event
TESAE	treatment-emergent serious adverse event
TGF- β	transforming growth factor beta
TIMI	TIMI Study Group, an academic research organization
T_{max}	time for C
TSS	Total Symptom Score
ULN	upper limit of normal
CCI	
US	United States
WBC	white blood cell
WOCBP	woman/women of childbearing potential

090177e1a1369fca\Approved\Approved On: 20-Jul-2024 06:57 (GMT)

## 1. VERSION HISTORY

Table 1. Summary of Changes

Version/ Date	Associated Protocol Amendment	Rationale	Specific Changes
1 21 Oct 2022	Original 23 Jun 2022	N/A	N/A
2 18 Oct 2024	Amendment 1 06 Jun 2023  Amendment 2 18 Jul 2024	
Open-label, PK cohort added in response to regulatory request.
 
Additional cohorts C and D added for lower dose and lower GDF-15
 
Daily diary removed.
 
Frequency of activity monitoring reduced.
 
Additional NT-proBNP timepoint added.
 
CCI endpoints/objectives added
 
AE outputs updated based on current guidance.
 
Interim Analysis details added.
	
 
Throughout: Protocol language updated; General updates to clarify relevant part of the study; Daily diary removed; total GDF-15 removed
 
2.2: Objectives updated to match protocol; clarification on definition of inadequate compliance; Additional protocol estimand wording added for safety and tertiary endpoints
 
2.3: Updated study description and schema added
 
3: Clarification of baseline definition
 
3.2.2: Further clarification of censoring
 
3.2.5.1/6.2.5.1: Medical evaluation of I-AEs updated
 
3.2.5.2: CFB in lipid panel endpoints added
 
3.2.5.3: Maximum changes in vitals signs added
 
3.3: Additional endpoints added; PGI-S and PGI-C clarified; %CFB in body weight removed; activity timepoints reduced and endpoints updated; definition of “compliant day” updated; healthy volunteer GDF-15 level corrected; method for dealing with BLQ values added; CCI added; clarification of clinical calculations; sections added for open-label, PK cohort endpoints
 
3.4: Modified BMI added
 
3.5: Maximum changes in QTcF added
 
4: Further clarification of analysis set definitions and details
 
5.1: Additional hypothesis testing wording added for open-label, PK cohort
 
5.2: General approach for analysis added; cohort added into analyses; Addition of ANCOVA, logistic regression without imputation, Cumulative incidence plots, Cox proportional hazards
 

			
 
• 5.3: Additional wording added for managing BLQ concentrations and missing data for PK parameters and screening data for PK Cohort participants
 
• 6.1.1: Clarification of cohort approach; Box and whisker plots removed; clarification of model terms; additional sensitivity analysis added
 
• 6.2/6.6: Clarification of cohort approach; sensitivity analysis added; Addition of a ponesgromab combined group in safety outputs (including ECGs); Summaries of injection site reactions added; Additional summaries for lipid panel endpoints
 
• 6.3: Additional endpoints added; sensitivity analysis added; Activity timepoints reduced and analysis changed to ANCOVA; Clarification of cohort approach; hsCRP, albumin and pre-albumin timepoints reduced and analysis changed to ANCOVA; total GDF-15 endpoint removed; CCI added; clarification that clinical outcomes are adjudicated; additional analysis for individual components of clinical composite; sections added for open-label, PK cohort endpoints
 
• 6.4: Subset analyses added
 
• 6.5: Baseline summaries updated; Additional detail added for participant discontinuations, prior/concomitant medications/procedures, and compliance
 
• 7: Details added for interim analyses
 
• 8: Reference added
 
• Appendix 4: Clarified when cohort is included in model; Example SAS code for ANCOVA, logistic regression without imputation, cumulative incidence plots and proportional hazards added
 
• Appendix 7: Abbreviations updated
 

--	--	--	---

## 2. INTRODUCTION

This statistical analysis plan (SAP) provides the detailed methodology for summary and statistical analyses of the data collected in Study C3651011 (the main cohort [Cohort A], the open-label, PK cohort [Cohort B], optional Cohort C, and optional Cohort D). This document may modify the plans outlined in the protocol; however, any major modifications of the primary endpoint definition or its analysis will also be reflected in a protocol amendment.

### 2.1. Modifications to the Analysis Plan Described in the Protocol

Not applicable.

### 2.2. Study Objectives, Endpoints, and Estimands

#### 2.2.1. Main Cohort (Cohort A), Cohort C and Cohort D

Type	Objectives	Endpoints	Estimands
Primary:	Primary:	Primary:	Primary:
Efficacy	
 
To compare the effect of ponesegromab 300 mg versus placebo, on HF disease-specific health status in participants with HF and serum GDF-15 concentrations <math>\geq 1000</math> pg/mL (Main Cohort [Cohort A]) only.
 
	
 
Change from baseline in KCCQ-23 CSS at Week 22.
 
	
 
Estimand 1 (similar to "hypothetical") is the difference between ponesegromab and placebo in mean change from baseline in KCCQ-23 CSS at Week 22, in study participants with HF and serum GDF-15 concentrations <math>\geq 1000</math> pg/mL, under the scenario of no discontinuation of study intervention and without the potential confounding effect of prohibited procedures or participants' non-compliance with dosing.
 

Secondary:	Secondary:	Secondary:	Secondary:
Efficacy	
 
To compare the effect of ponesegromab versus placebo on HF disease-specific overall health status in participants with HF and serum GDF-15 concentrations <math>\geq 1000</math> pg/mL.
 
	
 
Change from baseline in KCCQ-23 CSS, OSS, TSS, and physical limitation at Week 22.
 
	
 
Estimand 2 (similar to "hypothetical") is the difference between ponesegromab and placebo in mean change from baseline in each of KCCQ-23 CSS, OSS, TSS and physical limitation score at Week 22, in participants with HF and serum GDF-15 concentrations <math>\geq 1000</math> pg/mL, under the scenario of no discontinuation of study intervention and without the potential confounding effect of prohibited procedures or participants' non-compliance with dosing.
 

Efficacy	
 
To compare the effect of ponesegromab versus placebo on HF disease-specific health status in participants with HF
 
	
 
Responses as defined by a <math>\geq 5</math>-point increase from baseline in KCCQ-23 CSS, OSS, TSS, and physical limitation at Week 22.
 
	
 
Estimand 3 (similar to "hypothetical") is the odds ratio between ponesegromab and placebo on the proportion of participants with <math>\geq 5</math>-point increases from baseline in each of KCCQ-23 CSS,
 

	and serum GDF-15 concentrations CCI pg/mL.		OSS, TSS, and physical limitation score at Week 22, in participants with HF and serum GDF-15 concentrations CCI pg/mL, under the scenario of no discontinuation of study intervention and without the potential confounding effect of prohibited procedures or participants' non-compliance with dosing.
Efficacy	
 
To compare the effect of ponsegromab versus placebo on the physical function of participants with HF and serum GDF-15 concentrations CCI pg/mL.
 
	
 
Change from baseline in 6MWD at Week 22.
 
	
 
Estimand 4 (similar to "hypothetical") is the difference between ponsegromab and placebo in mean change from baseline in 6MWD at Week 22, in participants with HF and serum GDF-15 concentrations CCI pg/mL, under the scenario of no discontinuation of study intervention and without the potential confounding effect of prohibited procedures or participants' non-compliance with dosing.
 

Efficacy	
 
To compare the effect of ponsegromab versus placebo on fatigue reported by participants with HF and serum GDF-15 concentrations CCI pg/mL.
 
	
 
Change from baseline in PROMIS Fatigue 7a at Week 22.
 
	
 
Estimand 5 (similar to "hypothetical") is the difference between ponsegromab and placebo in mean changes from baseline in PROMIS Fatigue 7a at Week 22, in participants with HF and serum GDF-15 concentrations CCI pg/mL, under the scenario of no discontinuation of study intervention and without the potential confounding effect of prohibited procedures or participants' non-compliance with dosing.
 

Safety	
 
To describe the safety and tolerability of ponsegromab in participants with HF.
 
	
 
Incidence of TEAEs, TSEAEs, abnormal laboratory results, and vital signs.
 
	
 
There are no defined estimands for the incidence of TEAEs, TSEAEs, abnormal laboratory results, and vital signs, and these endpoints will be analyzed using Pfizer data standards as applicable.
 

Tertiary/Exploratory:	Tertiary/Exploratory:	Tertiary/Exploratory:	Tertiary/Exploratory:
Efficacy	
 
To compare the effect of ponsegromab 300 mg versus placebo, on HF disease-specific health status in participants with HF and any serum GDF-15 concentration.
 
	
 
Change from baseline in KCCQ-23 CSS, OSS, TSS, and physical limitation at Week 22.
 
Responses as defined by a <math>\geq 5</math>-point increase from baseline in KCCQ-23 CSS, OSS, TSS, and physical limitation at Week 22.
 
	
 
Not applicable.
 

Efficacy	
 
To compare the effect of ponsegromab 300
 
	
 
Change from baseline in 6MWD at Week 22.
 
	
 
Not applicable.
 

	mg versus placebo on the physical function of participants with HF and any serum GDF-15 concentration.		
Efficacy	
 
To compare the effect of ponesegromab 300 mg versus placebo on fatigue reported by participants with HF and any serum GDF-15 concentration.
 
	
 
Change from baseline in PROMIS Fatigue 7a at Week 22.
 
	
 
Not applicable.
 

Efficacy	
 
To compare the effect of ponesegromab versus placebo on HF disease-specific health status in participants with HF.
 
	
 
Response as defined by a <math>\geq 10</math>-point and <math>\geq 15</math>-point increase in KCCQ-23 CSS, OSS, TSS, and physical limitation at Week 22.
 
	
 
Not applicable.
 

Efficacy	
 
To describe the effect of ponesegromab on impressions of disease severity and change in participants with HF.
 
	
 
Absolute and change from baseline in PGI-S at Week 22.
 
Absolute PGI-C at Week 22.
 
	
 
Not applicable.
 

Efficacy	
 
To compare the effect of ponesegromab versus placebo on body weight in participants with HF.
 
	
 
Change from baseline in body weight at Week 22.
 
	
 
Not applicable.
 

Efficacy	
 
To compare the effect of ponesegromab versus placebo on daily activity measures based on accelerometry in participants with HF.
 
	
 
Change from baseline in daily activity measures based on accelerometry at Week 22.
 
	
 
Not applicable.
 

Pharmacokinetics	
 
To evaluate the PK of ponesegromab in participants with HF.
 
	
 
Serum unbound and total ponesegromab concentrations on Day 1 (predose) and Weeks 4, 8, 12, 16, 20, 22, 24, and 32.
 
	
 
Not applicable.
 

Biomarkers	
 
To compare the effect of ponesegromab versus placebo on GDF-15 concentrations in participants with HF.
 
	
 
Serum concentrations of GDF-15 on CCI [REDACTED]
 
	
 
Not applicable.
 

Immunogenicity	
 
To characterize the immunogenicity of ponesegromab in participants with HF.
 
	
 
Incidence of anti-ponesegromab antibodies, and neutralizing antibodies.
 
	
 
Not applicable.
 

Biomarkers	
 
To compare the effect of ponesegromab versus placebo on markers to check HF
 
	
 
Fold change from baseline in NT-proBNP, hsCRP, albumin and pre-albumin at Week 22.
 
	
 
Not applicable.
 

	risk, acute MI, inflammation, and nutritional status in participants with HF.		
Efficacy	
 
To compare the effect of ponesegromab versus placebo on CCI in participants with HF.
 
	
 
Fold change from baseline in CCI at Weeks 12 and 22.
 
Fold change from baseline in CCI at Weeks 12 and 22 (Cohorts C and D only).
 
	
 
Not applicable.
 

Efficacy	
 
To compare the effect of ponesegromab versus placebo on clinical outcomes of cardiovascular death, hospitalization for HF, or urgent HF visit and on days alive and out of the hospital in participants with HF.
 
	
 
Hierarchical composite endpoint:               
 
Time to cardiovascular death;
 
Number of worsening HF events (hospitalization for HF, or urgent HF visit);
 
Time to first worsening HF event (hospitalization for HF, or urgent heart visit);
 
Change from baseline in KCCQ-23 CSS at Week 22.
 
 
 
Time to first occurrence of the clinical composite of cardiovascular death, hospitalization for HF, or urgent heart visit.
 
Total number of days alive and out of the hospital over 22 weeks.
 
Total number of hospitalizations for HF and urgent HF visits over 22 weeks.
 
	
 
Not applicable.
 

## 2.2.2. Open-label, PK Cohort (Cohort B)

Type	Objectives	Endpoints	Estimands
Secondary:	Secondary:	Secondary:	Secondary:
Safety	
 
To evaluate the safety and tolerability of ponesegromab in participants with HF and elevated circulating GDF-15 concentrations.
 
	
 
Incidence of TEAEs, TSEAEs, abnormal laboratory results, and vital signs.
 
	
 
There are no defined estimands for the incidence of TEAEs, TSEAEs, abnormal laboratory results, and vital signs, and these endpoints will be analyzed using Pfizer data standards as applicable.
 

Tertiary/Exploratory:	Tertiary/Exploratory:	Tertiary/Exploratory:	Tertiary/Exploratory:
Pharmacokinetics	
 
To evaluate the PK of ponesegromab following repeated SC administration in participants with HF and elevated circulating GDF-15 concentrations.
 
	
 
Serum unbound and total ponesegromab PK parameters after 1st dose on Day 1 and 4th dose on Day 85: AUC0-∞, Cmax, Tmax and as data permit, t1/2, CL/F, Vz/F, PTR after 4th dose.
 
	
 
There are no defined estimands for PK endpoints.
 

Biomarkers	
 
To characterize the effect of ponesegromab on circulating GDF-15 concentrations in participants with HF and elevated circulating GDF-15 concentrations.
 
	
 
Serum concentrations of GDF-15 on CCI [REDACTED]
 
	
 
Not applicable
 

Immunogenicity	
 
To characterize the immunogenicity of ponesegromab in participants with HF and elevated circulating GDF-15 concentrations.
 
	
 
Incidence of ADA, and NAb.
 
	
 
Not applicable.
 

Biomarkers	
 
To evaluate the effect of ponesegromab on NT-proBNP in participants with HF and elevated circulating GDF-15 concentrations.
 
	
 
Fold change from baseline in NT-proBNP at Weeks 12 and 16.
 
	
 
Not applicable.
 

### 2.2.3. Primary Estimand(s)

Estimands related to the HF disease-specific health status primary objective (Main Cohort [Cohort A] only):

*Estimand 1 (similar to “hypothetical”) is intended to provide a population level estimate of the treatment effect on the change from baseline in KCCQ-23 CSS for ponesegromab compared with placebo in all evaluable participants in the Main Cohort (Cohort A), under the scenario of no discontinuation of study intervention and without the potential confounding effect of prohibited procedures or participants’ non-compliance with dosing (ie, using the censored analysis set for the Main Cohort (Cohort A) as defined in Section 4).*

- Population: Participants with HF, elevated circulating GDF-15 concentrations and KCCQ-23 CSS <75.
- Endpoint: Change from baseline in KCCQ-23 CSS at Week 22.
- Intercurrent Events:
  - Discontinuation of study intervention: Data collected after a participant has discontinued study intervention will be censored and treated as missing data.

- b. *Prohibited procedures: Data collected after a participant has undergone prohibited procedures, that would modulate the primary endpoint, will be censored and treated as missing data. Any procedures will be reviewed prior to database lock to determine which would be classed as “prohibited” for this estimand.*
- c. *Inadequate compliance: Data collected after a participant has missed a dose, or has received an incomplete dose, will be censored and treated as missing data. For participants who resume (complete) dosing, their subsequent data may be included in the analysis following a review of their compliance prior to database lock.*

*Missing data due to censoring, study withdrawal or other reasons, are assumed to be missing at random in the analysis.*

- *Population-level summary: Difference in mean change from baseline for the KCCQ-23 CSS at Week 22 between ponsegromab and placebo.*

**Estimand 1b** (similar to “treatment policy”) is intended to provide a population level estimate of the treatment effect on the change from baseline in KCCQ-23 CSS for ponsegromab compared with placebo in all evaluable participants in the Main Cohort (Cohort A), regardless of discontinuation of study intervention, dosing compliance or prohibited procedures (ie, using the complete analysis set for the Main Cohort (Cohort A) as defined in Section 4).

- **Population:** Participants with HF, elevated circulating GDF-15 levels and KCCQ-23 CSS <75
- **Endpoint:** Change from baseline in KCCQ-23 CSS at Week 22
- **Intercurrent Events:** There are no changes made based on intercurrent events. For participants who discontinue study intervention, receive a prohibited procedure and/or miss a dose or receive an incomplete dose, all observations post-discontinuation, post-procedure or post-missed/incomplete dose will be included in the analysis set.
- **Population-level summary:** Difference in mean change from baseline for the KCCQ-23 CSS at Week 22 between ponsegromab and placebo

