2.2.1.1. GDF-15 and Heart Failure

GDF-15, also known as MIC-1, is a member of the TGF- β superfamily. In healthy individuals, GDF-15 is expressed and secreted at low concentrations by a range of cell types. In response to acute and cellular stressors, such as inflammation, oxidative stress, and cellular senescence, GDF-15 expression increases.^{3,4,5,6} As such, circulating GDF-15 concentrations are markedly elevated in several chronic conditions such as cancer, HF, COPD, and CKD, compared to concentrations in healthy individuals.^{7,8,9,10,11}

In patients with HF, GDF-15 is a well-established prognostic biomarker of cardiovascular morbidity and mortality.¹² Circulating GDF-15 concentrations are highly associated with HF symptom severity, functional status, and exercise capacity. Moreover, elevated GDF-15 concentrations predict an increased risk of death and adverse HF events in patients with HF.¹³ It is hypothesized that ponsegromab may neutralize effects of GDF-15 and thereby improve symptoms in HF patients.

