#### 2.2.4. Secondary Estimand(s)

*The secondary estimands are applied to the comparisons between each ponsegromab dose and placebo. Data from the Main Cohort (Cohort A) will be used for comparisons between ponsegromab 300 mg and placebo. Data from the Main Cohort (Cohort A) and Cohort C, combined (ie, Cohort A + Cohort C), will be used for comparisons between ponsegromab 100, 200 and 300 mg and placebo.*

Estimand related to the HF disease-specific health status secondary objective (Main Cohort [Cohort A]  $\pm$  Cohort C):

Estimand 2 will be similar to Estimand 1, except for the following:

- Endpoint: Change from baseline in each of KCCQ-23 CSS\*, OSS, TSS and physical limitation score at Week 22.
- Population-level summary: Difference in mean change from baseline for the KCCQ-23 CSS, OSS, TSS, or physical limitation score at Week 22 between ponsegromab and placebo.

\* Note: For KCCQ-23 CSS, comparisons between ponsegromab 100 or 200 mg and placebo are based on data from the Main Cohort (Cohort A) and Cohort C combined, only.

Estimand related to the HF disease-specific health status (responses as defined by a  $\geq 5$ -point increase from baseline) secondary objective (Main Cohort [Cohort A]  $\pm$  Cohort C):

Estimand 3 will be similar to Estimand 1, except for the following:

- Endpoint: Response as defined by a  $\geq 5$ -point increase in each of KCCQ-23 CSS, OSS, TSS, and physical limitation score at Week 22.
- Population-level summary: Odds ratio for the proportion of study participants with  $\geq 5$ -point increase in KCCQ-23 CSS, OSS, TSS, and physical limitation score at Week 22 between ponsegromab and placebo.

Estimand related to the physical function secondary objective (Main Cohort [Cohort A]  $\pm$  Cohort C):

Estimand 4 will be similar to Estimand 1, except for the following:

- Endpoint: Change from baseline in the 6MWD at Week 22.
- Population-level summary: Difference in mean change from baseline for the 6MWD at Week 22 between ponsegromab and placebo.

Estimand related to the Fatigue secondary objective (Main Cohort [Cohort A]  $\pm$  Cohort C):

Estimand 5 will be similar to Estimand 1, except for the following:

- Endpoint: Change from baseline in PROMIS Fatigue 7a at Week 22.
- Population-level summary: Difference in mean change from baseline for PROMIS Fatigue 7a at Week 22 between ponsegromab and placebo.

Estimands related to the safety and tolerability secondary objective (All Cohorts):

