#### 3.2.2. Responses as defined by a $\geq 5$ -point increase from baseline in KCCQ-23 CSS, OSS, TSS, and physical limitation at Week 22 (Cohorts A and C)

See Section 3.1.1.

Each of these endpoints will have two levels: 'Response' and 'Non-response'. The former will be based on participants having a  $\geq 5$ -point increase from baseline in KCCQ-23 CSS, OSS, TSS, or physical limitation, respectively, at Week 22. Otherwise, participants will be classed as having a 'Non-response'. Participants with an intercurrent event of premature discontinuation of IP, prohibited procedure or inadequate compliance prior to Week 22 will have their Week 22 value censored (if not missing). Missing or censored values at Week 22 will be imputed as described in Section 5.3. Participants who die during the study will be classed as having a 'Non-response' after imputation.

These endpoints will be calculated similarly for all other post-baseline timepoints.

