#### 3.2.3. Change from baseline in 6MWD at Week 22 (Cohorts A and C)

*The 6MWT is a submaximal exercise test that entails measurement of distance walked over a span of 6 minutes. The 6MWD (distance traveled in meters) provides a measure for integrated global response of multiple cardiopulmonary and musculoskeletal systems involved in exercise.*

The change from baseline in 6MWD will be calculated for all post-baseline timepoints with a valid test result.

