##### 6.1.1.1. Main Analysis

This analysis will be performed on the censored analysis set, as defined in Section 4.

Absolute values and changes from baseline in the KCCQ-23 CSS score will be summarized descriptively by treatment group and timepoint, as described in Section 5.2.1. Tables will include baseline and all post-baseline timepoints.

*Change from baseline in KCCQ-23 CSS at Week 22 will be analyzed using Estimand 1 and an MMRM model, as described in Section 5.2.3. The MMRM model will be fitted to the change from baseline at all post-treatment timepoints up to Week 22 using the Censored analysis set (as defined in Section 4) from Cohort A participants only. Additional terms for baseline LVEF, log CCI GDF-15 concentrations from SV1 and baseline log NT-proBNP will be fitted in the model.*

Additional plots of LS means and differences (including 90% CIs for both), for Week 22 only, will be produced over treatment (for the primary endpoint only).

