**6.2.3. Change from baseline in 6MWD at Week 22 (Cohorts A and C)**

Summaries and analyses will use efficacy approaches 1 and 3, as described in Section 5.2.

6MWD will be summarized and analyzed across all timepoints, in a similar manner to the main analysis of the primary endpoint, as outlined in Section 6.1.1.1. This analysis will

estimate the treatment effect related to Estimand 4 (as described in Section 2.2.4). Note that for efficacy approach 3, cohort will be included as a term in the statistical model.

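### Read literally, the responder rule turns deaths after Week 22 into Week 22 failures; and no planned mean difference in KCCQ-23 CSS or 6MWD accounts for death before Week 22

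*SAP*

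**What the plan says.** **Responder endpoints.** SAP 3.2.2 states: "Participants who die during the study will be classed as having a 'Non-response' after imputation". Section 3.3.5 (10- and 15-point responses) and section 5.3.4 (multiple imputation) repeat the rule, also without a Week 22 limit. SAP 2.3 gives a 22-week treatment period, a 10-week follow-up and 32 weeks in total. The note in Appendix 4 is worded differently: it concerns a participant who discontinues because of death and whose value has been imputed. The example code beneath it sets response from the Week 22 change alone and contains no step for death.

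**Continuous endpoints.** Estimand 1 (SAP 2.2.3; Protocol 9.1.1.1) is hypothetical, "under the scenario of no discontinuation of study intervention and without the potential confounding effect of prohibited procedures". It lists three intercurrent events: stopping study drug, prohibited procedures and inadequate compliance. Death is not among them. The rest is covered by one sentence: "Missing data due to censoring, study withdrawal or other reasons, are assumed to be missing at random in the analysis". SAP 6.1.1.1 then says: "Change from baseline in KCCQ-23 CSS at Week 22 will be analyzed using Estimand 1 and an MMRM model". Estimands 2 and 5 inherit this, as does the walk test: "Estimand 4 will be similar to Estimand 1, except for the following", where the exceptions are endpoint and summary only. SAP 3.2.3 adds: "The change from baseline in 6MWD will be calculated for all post-baseline timepoints with a valid test result". Section 6.2.3 adds: "6MWD will be summarized and analyzed across all timepoints, in a similar manner to the main analysis of the primary endpoint".

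For the primary endpoint, SAP 6.1.1.2 plans two further analyses: Estimand 1b on the complete set, which makes no adjustment for intercurrent events, and a restriction to baseline CSS below 75.

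**The concern.** Deaths are to be expected in this population. Entry requires NYHA class II-IV and NT-proBNP of at least 400 pg/mL, and the main cohort is enriched for a marker about which Protocol 2.2.1.1 says "elevated GDF-15 concentrations predict an increased risk of death and adverse HF events in patients with HF".

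Two separate things are at stake. First, a secondary endpoint defined at Week 22 should not depend on what happens between Week 22 and Week 32. As worded, two programmers could derive different responder odds ratios from the same data, one following 3.2.2 and 5.3.4, the other following Appendix 4.

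Second, a participant who dies before Week 22 has no Week 22 score or walk distance. The MMRM target for that participant is in effect what participants with a similar history who remained in the data would have scored. If deaths differ between arms, the mean differences in KCCQ-23 CSS and 6MWD will not show it.

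**Working it through.** **Plan's own figure.** Protocol 9.5: 190 randomised per arm with 15% discontinuation gives 190 x 0.85 = 161.5, against approximately 161 stated. This agrees. The 15% does not separate deaths. The basis of the sample size (effect, SD, power) is redacted and is not questioned here.

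**Responder rule.** Compare the texts for a participant who dies in Week 28:

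| Week 22 score | 3.2.2, 3.3.5, 5.3.4 read literally | Appendix 4 note | Appendix 4 code |
|---|---|---|---|
| Observed, gain of at least 5 | Non-response | Response (nothing was imputed) | Response |
| Missing or censored, imputed gain of at least 5 | Non-response | Non-response | Response |

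So the narrower note also needs a date limit: in the second row the participant was alive at Week 22.

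Share of the window: Week 22 is Day 155 and Week 32 is Day 225. (225 - 155)/(225 - 1) = 70/224 = 31%. With a constant death rate (assumption), about 31% of deaths during the study fall after Week 22. With assumed Week 22 mortality p, mortality to Week 32 is 1 - (1 - p)^(224/154):

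| p at Week 22 | to Week 32 | extra | extra per 190 |
|---|---|---|---|
| 2% | 2.9% | 0.9% | 1.7 |
| 4% | 5.76% | 1.76% | 3.4 |
| 6% | 8.6% | 2.6% | 5.0 |

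Only those who would otherwise be responders change category.

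For the odds ratio, assume a normal change with mean +4 on placebo and +9 on active, and Week 22 mortality of 2% on placebo and 6% on active:

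| SD | deaths as MAR | deaths to Week 22 as non-response | deaths to Week 32 as non-response |
|---|---|---|---|
| 15 | 1.71 | 1.52 | 1.45 |
| 20 | 1.49 | 1.35 | 1.29 |

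With 4% in both arms and SD 15, the last two columns are 1.66 and 1.65.

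**Mean difference.** Let b be mean baseline CSS, m_T and m_C the mean changes on active and placebo under MAR, and p_T and p_C mortality by Week 22. If death is scored as CSS 0, its change is -b. The treatment difference then moves by

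shift = -p_T(b + m_T) + p_C(b + m_C).

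This takes those who die to have the same mean baseline and modelled change as the others in their arm. With m_T = m_C = 5 it reduces to (p_C - p_T)(b + 5). Per percentage point of imbalance, for b = 40 to 60: 0.01 x 45 = 0.45 to 0.01 x 65 = 0.65. For 3 percentage points: 1.35 to 1.95.

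With m_C = 4 and m_T = 9, so a MAR difference of 5.0:

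| Mortality, placebo v active | Difference with death = 0, b = 40 to 60 |
|---|---|
| Equal, 2% to 6% | 4.9 to 4.7 |
| 6% v 4% | 5.7 to 6.1 |
| 4% v 6% | 3.8 to 3.4 |
| 2% v 6% | 2.9 to 2.1 |

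With equal mortality p the shift is -5p, which at 6% is -0.3.

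**What already counts death.** The secondary responder analysis covers death from any cause, on four KCCQ scores, in binary form. The win ratio (SAP 5.2.9, 6.3.14.1) is tertiary, compares 300 mg with placebo only and uses cardiovascular death. The Cox models cover cardiovascular death and heart failure events. Days alive and out of hospital counts death from any cause but is descriptive. None gives a mean CSS or 6MWD difference.

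**The case against.** The strongest reply has four parts.

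1. The hypothetical strategy is declared openly. Using one strategy for a continuous mean and another for a binary response is not in itself an error. This stands, and it is why the primary MMRM should remain.

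2. The plan already has an alive-and-improved analysis of the primary instrument at secondary level, with p-values. This also stands. A reader might infer that the win ratio is the only analysis joining death with KCCQ; that is wrong. What is missing is an analysis on the mean scale, and any such analysis for 6MWD.

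3. A reader might infer that the SAP firmly requires follow-up deaths to overwrite observed Week 22 responses, and at every earlier visit too. The documents do not support that. The rule applies after imputation, Appendix 4 ties it to an imputed value, and SAP 6.2.2 tabulates responses by visit with no imputation. Section 6.3.5 likewise summarises the 10- and 15-point responses with no imputation. The defect is conflicting wording, one reading of which gives a wrong result.

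4. A reader might infer that excess deaths on active drug would go unnoticed. They would not: disposition by arm includes death, all deaths are adjudicated, and the E-DMC sees unblinded safety data. The MMRM also uses observed scores from before death. It remains true that these sources do not tell the reader how far the KCCQ or 6MWD difference depends on the treatment of death.

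Eligibility excludes recent decompensation and participants whom the investigator judges to have a life expectancy under one year, so mortality may be low.

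**Conclusion.** Both parts hold and both can be settled in the SAP. The responder rule is ambiguous across 3.2.2, 3.3.5, 5.3.4 and Appendix 4, and its literal reading lets a death after Week 22 change a Week 22 result. Separately, death has no stated strategy in Estimands 1, 1b, 2, 4 or 5. Classing it as discontinuation would change nothing, since that rule censors and returns to MAR. Estimand 1b does not help, since death leaves no later observation to include.

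The size is conditional. The documents give no death rate, mean baseline, expected change or SD, and scoring death as 0 is a convention. On the assumptions shown, the CSS difference moves by 0.45-0.65 points per percentage point of mortality imbalance, and by at most about 0.3 points if mortality is equal at 2-6%. The concern is therefore imbalance, not death as such.

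It would go too far to say that the primary analysis treats the dead as alive and on drug. The MMRM imputes no explicit value; that phrase describes only its implicit target under the hypothetical estimands, and under Estimand 1b the target is not necessarily on drug. The primary analysis is not invalidated.

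**What to change.** 1. In SAP 3.2.2, 3.3.5, 5.3.4 and the Appendix 4 note, limit the non-response rule to deaths on or before the Week 22 visit. Add the matching step to the Appendix 4 code after response is derived. All four places must change together, or a new inconsistency is created. The cost is wording and a line or two of code.

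2. Keep the primary MMRM. Add to 6.1.1.2 and 6.2.3 one supplementary analysis in which death on or before Week 22 is an outcome, for example a worst-rank analysis, or KCCQ-23 CSS 0 and 6MWD 0 m. Protocol 9.1.1.1 already allows alternative estimands for robustness, to be detailed in the SAP. The cost is one extra table with a somewhat noisier estimate.

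3. A sentence in 2.2.3 and 2.2.4 saying how each estimand handles death would make the difference between Estimand 3 and the others explicit.

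Settle the choice before database lock, so that it does not depend on deaths by arm.
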